8.2.3.3 EXPECTEDNESS

All Adverse Events (AEs) must have their relationship to the study intervention assessed by a qualified physician who is part of the study team based on temporal relationship and their clinical judgment. The degree of certainty about causality will be graded using the categories below.

- **Definitely Related** – There is clear evidence to suggest a causal relationship, and other possible contributing factors can be ruled out. The clinical event, including an abnormal laboratory test result, occurs in a plausible time relationship to study intervention administration and cannot be explained by concurrent disease or other drugs or chemicals. The response to withdrawal of the study intervention should be clinically plausible.
- **Probably Related** – There is evidence to suggest a causal relationship, and the influence of other factors is unlikely. The clinical event, including an abnormal laboratory test result, occurs within a reasonable time after administration of the study intervention, is unlikely to be attributed to concurrent disease or other drugs or chemicals, and follows a clinically reasonable response on withdrawal.
- **Possibly Related** – There is some evidence to suggest a causal relationship (e.g., the event occurred within a reasonable time after administration of the study intervention). However, other factors may have contributed to the event (e.g., the participant's clinical condition, other concomitant events).
- **Unlikely to be related** – A clinical event, including an abnormal laboratory test result, whose temporal relationship to study intervention administration makes a causal relationship improbable (e.g., the event did not occur within a reasonable time after administration of the study intervention) and in which other drugs or chemicals or underlying disease provides plausible explanations (e.g., the participant's clinical condition, other concomitant treatments).
- **Unrelated** – The AE is completely independent of study intervention administration, and/or evidence exists that the event is definitely related to another etiology.

8.2.3.2 RELATIONSHIP TO STUDY INTERVENTION

A qualified physician who is part of the study team will be responsible for determining whether an Adverse Event (AE) is expected or unexpected. An AE will be considered unexpected if the nature, severity, or frequency of the event is not consistent with the risk information previously described for the study intervention.

8.2.4 TIME PERIOD AND FREQUENCY FOR EVENT ASSESSMENT AND FOLLOW-UP

All Adverse Events (AEs) or Serious Adverse Events (SAEs) due to IVR stimulation resolve as soon as the stimulation stops²⁵. Investigators will follow-up the participant at 24 hours by phone or email assessing the severity of the AEs using the VRISE questionnaire

AE reporting will begin at the time of signing of the informed consent (screening) and will continue until discharge from the study. AEs will be elicited by:

- spontaneous report by participants and/or parents,
- by 3 consecutive VRISE scores < 25,
- by observation (by the investigators and/or healthcare staff).

AEs will be documented in the source documents and the eCRF within 24 hrs.

All AEs and SAEs occurring while on study must be documented regardless of relationship. Information to be collected includes event description, date and time (if possible) of onset, date and time (if possible) of resolution/stabilization of the event, outcome, and the assessment of seriousness, expectedness, relationship to study intervention and severity by a delegated qualified physician.

Any baseline condition recorded in the medical history that deteriorates at any time during the study, will be recorded as an AE or SAE.

Changes in the severity of an AE will be documented to allow an assessment of the duration of the event at each level of severity to be performed.

Events will be followed for outcome information until resolution or in the opinion of the PI or qualified physician delegate, the participant is stable and does not require further follow-up, or the participant is deemed lost to follow-up.

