1.2 SCHEMA

1.3 SCHEDULE OF ACTIVITIES (SOA)

	Inclusion	Baseline	Treatment																Follow-up	
Day	0	0	1	3	5	7	9	11	13	14	15	17	19	21	23	25	27	28	58	200
Visit #		1								2								3	4	5
Fixation stability		X								X								X	X	X
BCVA		X								X								X	X	X
Contrast sensitivity		X								X								X	X	X
MNREAD test		X								X								X	X	X
CVFQ		X								X								X	X	X
Humphrey Full Field 120		X																X	X	X
Esterman binocular		X																X	X	X
VRIFE	X		X	X	X	X	X	X	X	X	X	X	X	X	X	X	X			
IVR	X		X	X	X	X	X	X	X	X	X	X	X	X	X	X	X			

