8.2.2 DEFINITION OF SERIOUS ADVERSE EVENTS (SAE)

An Adverse Event (AE) is any untoward medical occurrence associated with the use of an intervention in a study participant, which does not necessarily have a causal relationship with the intervention. An AE can therefore be any unfavourable and unintended sign (including an abnormal laboratory finding), symptom or disease temporally associated with the use of the intervention, whether or not considered related to the investigational intervention.

Stable chronic conditions which are present prior to entry in the study and do not worsen are not considered AE. These pre-existing conditions will be documented in the participant's medical history.

AEs will be the primary safety endpoints. Known AEs induced by IVR stimulation are nausea, dizziness and disorientation. The severity of these AEs will be scored using the validated VRISE questionnaire. A VRISE score < 25 is considered as an AE. Three (3) consecutive VRISE scores < 25 will lead to the withdrawal of the study.

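### Outside the session-linked VRISE questionnaire and the visual tests at visits, adverse events are recorded only if volunteered or noticed, so rates for those events are biased downward

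*Combined protocol and SAP*

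**What the plan says.** The text defining an adverse event (AE), under heading 8.2.2, states: "AEs will be the primary safety endpoints". Section 8.2 announces that safety will be judged by AEs, withdrawals because of AEs, and AE rates. Section 8.2.4 sets a wide scope, running from informed consent to discharge: "All AEs and SAEs occurring while on study must be documented regardless of relationship".

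Section 8.2.4 then lists three routes by which AEs are elicited: "spontaneous report by participants and/or parents", "by 3 consecutive VRISE scores < 25", and "by observation (by the investigators and/or healthcare staff". It also provides a contact at 24 hours, which uses VRISE to follow up an AE.

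On virtual-reality symptoms the plan is more active. Section 8.2.2 says: "Known AEs induced by IVR stimulation are nausea, dizziness and disorientation". It has VRISE score their severity and adds: "A VRISE score < 25 is considered as an AE". Section 4.1 has the child answer VRISE (five items, each scored 1 to 7) before and after every session, and section 8.2.3 presents it as the tool for assessing AEs related to the stimulation.

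The schedule in section 1.3 has no AE row. Its VR-symptom row (printed VRIFE, taken here to be VRISE) has one entry at inclusion and 15 in treatment, the last on day 27. It is blank on days 28, 58 and 200. Section 8.1 lists only visual tests and quality of life for the visits. Section 9.4.4 summarises VRISE scores and no AE counts.

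**The concern.** The scope and the method do not match. The plan wants every AE over about seven months, related or not, but apart from VRISE and the visual tests it relies on a family volunteering the event or on staff noticing it. Training takes place at home, out of staff sight. A parent who does not connect a problem with the headset, or whose child has recovered by the next visit, has no occasion in the plan to mention it.

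That loss goes one way: unprompted collection can miss events, but it does not add any. The AE rate announced in section 8.2 is therefore too low for the events concerned. This matters because the plan says the approach has never been tested in children, and section 2.3 asserts that enrolled patients face no risks. A report of no AEs from this pilot would be read as support for that assertion.

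**Working it through.** **1. Which events are prompted for.** Setting sections 1.3, 4.1, 7, 8.1 and 8.2 side by side:

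| Event | Prompted enquiry or test | Otherwise |
|---|---|---|
| Nausea, dizziness, disorientation around a session | VRISE before and after each session | Volunteered, observed |
| Visual worsening | Visual tests at visits 2 to 5; section 7 makes new clinically relevant findings AEs | Volunteered |
| Other events during treatment, and events between sessions | None (24-hour VRISE only after an AE already known, or after withdrawal) | Volunteered, observed at visits |
| Non-visual events, days 28 to 200 | None | Volunteered, observed at visits |

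The documents do not give VRISE's recall period. The third row assumes that the pre-session score describes the child at that moment.

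**2. How much enquiry there is, and when.** VRISE: 15 sessions × 2 = 30 per child, or 300 for 10 children. After the end of treatment: 200 − 28 = 172 days, and 172/200 = 86% of the schedule, with no VRISE planned.

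**3. What zero recorded events would mean (illustration, only for events VRISE does not solicit).** The plan gives no AE rate to reproduce. Section 9.2 sets 10 patients without a calculation. Let p be the true risk per child and c the chance that an affected child is detected, with children independent. The one-sided 95% upper limit after 0 of 10 solves (1 − cp)^10 = 0.05, so p = (1 − 0.05^(1/10))/c = 0.259/c.

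- c = 1: 0.259, or 26%
- c = 0.7 (assumed): 0.259/0.7 = 0.370, or 37%
- c = 0.5 (assumed): 0.259/0.5 = 0.518, or 52%

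The 26% comes from having 10 children. Only the rise above it comes from the method of collection.

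The chance of recording nothing at a given true risk is (1 − cp)^10. With p = 0.20 (assumed):

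- c = 1: 0.80^10 = 0.11
- c = 0.5: 0.90^10 = 0.35
- c = 0.25: 0.95^10 = 0.60

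**4. One low score or three.** Section 8.2.2 makes a single VRISE score below 25 an AE, whereas section 8.2.4 elicits AEs by three in a row. Take the 15 post-session scores, independent, each with an assumed 10% chance of being low. At least one low score has probability 1 − 0.9^15 = 0.79. A run of three, by exact recursion over the 15 scores, has probability 0.012. At an assumed 5% the pair is 0.54 and 0.0015; at 20% it is 0.97 and 0.083. Low scores in one child are probably correlated, which makes runs likelier than shown. The AE count still depends heavily on which sentence is followed.

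**The case against.** The strongest reply is that the plan does ask about the effects that matter most. Nausea, dizziness and disorientation are the known AEs of the intervention, and VRISE prompts for them about 30 times per child. A clean record for those symptoms around sessions would not come from failing to ask. This stands, and it limits the point.

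Other parts of the reply also stand. Visits 2 to 5 last 1.5 hours each and repeat visual testing, so visual worsening is looked for. A parent is called after missed or incomplete sessions (section 4.1), and concomitant medication is recorded (section 6.5), although neither is an AE question. The missing AE row is weak evidence taken alone, because the schedule also has no row for consent or concomitant medication. Here it agrees with the 8.2.4 list and with section 8.1, neither of which contains an AE question. Counting all 172 follow-up days equally overstates what is lost on device effects, since section 8.2.4 says these resolve when stimulation stops. Section 8.2.4 nevertheless asks for all AEs, related or not, until discharge. Finally, the success criteria in section 9.1 concern session completion, VRISE runs and cybersickness dropouts, so an open AE question would not change that decision.

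A reader might infer that AEs as a whole go unasked and that any clean safety record would be an artefact. The documents do not support that, because VRISE is prompted collection. Nor do they support calling staff observation haphazard, or applying the 37% and 52% limits to symptoms VRISE solicits.

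**Conclusion.** The concern holds for three groups: events that neither VRISE nor the visual tests cover, events between sessions, and non-visual events from day 28 to day 200. For these, the method in section 8.2.4 falls short of the scope set in the same section. The AE rate is biased downward, and a report of no AEs would partly reflect not asking.

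The direction follows from the text; the size does not. The detection fractions are assumptions, and the limits of 37% and 52%, against 26% with full detection, only show how quickly a zero loses meaning. For nausea, dizziness and disorientation around sessions the concern does not apply, but the recorded count remains undefined until sections 8.2.2 and 8.2.4 agree on one low score or three.

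The feasibility decision is unaffected. What is weakened is the safety statement that the pilot could make.

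**What to change.** - **Section 8.2.4:** keep spontaneous report and add one standard, non-leading question on any health problem since the last contact. Ask it at visits 2 to 5, at the parent calls after missed sessions and at the 24-hour contacts. Record a negative answer as well.
- **Section 1.3:** add an AE row covering visits 2 to 5.
- **Sections 8.2.2 and 8.2.4:** reconcile them on whether one VRISE score below 25, or three consecutive ones, produces a recorded AE.
- **Section 9.4.4:** report AE counts and rates, with solicited and spontaneous events shown separately, alongside the VRISE summary. Otherwise the added information would not reach the planned safety analysis.

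The cost is one question at contacts that already take place, plus one line on the case report form. The downside is that more minor, unrelated events will be recorded, although section 8.2.4 already asks for them.

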8.2.5 ADVERSE EVENT REPORTING

AE will be reported to The Hospital for Sick Children Research Ethics Board according to The Hospital for Sick Children's Adverse Event Reporting Requirements.

8.2.6 SERIOUS ADVERSE EVENT REPORTING

Adverse events will be reported to The Hospital for Sick Children Research Ethics Board according to The Hospital for Sick Children's Adverse Event Reporting Requirements.

8.2.7 REPORTING EVENTS TO PARTICIPANTS

Participants and/or their parent/legal guardian will be informed in a timely manner of any new information, including safety information, that is relevant to that participant's willingness to continue participation. The communication of this information will be documented through a revised REB approved Informed Consent Form, where possible, based on the timeliness of the information.

In the event that a study procedure detects a new clinically important secondary finding/incidental finding, the qualified physician will notify the Most Responsible Physician (MRP) physician at SickKids (if the participant is being treated at SickKids) or request the participant's family doctor's name and contact information in order to arrange medical follow-up to interpret the significance of the findings.

8.2.8 REPORTING OF PREGNANCY

If a participant becomes pregnant, the study drug will be permanently discontinued, and the participant will complete the evaluations/procedures for the early termination visit.

9 STATISTICAL CONSIDERATIONS

9.1 STATISTICAL HYPOTHESES

- Primary Endpoint(s):

Feasibility is considered when the following primary endpoints criteria are met:

1. $\geq 8/10$ patient (80%) completed the protocol.
2. IVR stimulation protocol is considered complete if the patient performed ≥ 12 sessions out of 15.
3. ≤ 3 consecutive VRISE score < 25 per patient during the treatment period.
4. ≤ 2 dropouts (20%) for cybersickness (discomfort symptoms experienced in VR)

- Secondary Endpoint(s):

Secondary endpoint measures will be performed at Toronto Western hospital during baseline (visit 1), after 2 weeks (visit 2), after treatment at 4 weeks (visit 3) and at 1-month (visit 4) and 6 months (visit 5) follow-up. Results will be compared to baseline.

Visual acuity:

- Best Corrected Visual Acuity (BCVA) scores for distance and near vision – ETDRS/Colenbrander charts.
- Fixation stability - MAIA microperimeter, CentreVue
- Contrast sensitivity – FACT test.

Field of Vision:

- Humphrey full field 120 – Humphrey Field Analyzer 3, Zeiss
- Esterman binocular field - Humphrey Field Analyzer 3, Zeiss

Reading Speed:

- Minnesota Low Vision Reading - MNREAD test.

Quality of life:

- Children's Vision Function Questionnaire (39 questions)

- Exploratory Endpoint(s):

None

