5.2 EXCLUSION CRITERIA

An individual who meets any of the following criteria will be excluded from participation in this study:

1. Ocular diseases
2. Both eyes with media opacity that impairs microperimetry testing.
3. Inability to perform during testing and training.
4. Consumption of psychoactive drugs.
5. 3 consecutive VRIFE scores < 25 at inclusion.
6. History of vertigo or dizziness
7. Prior vision rehabilitation interventions.

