7.2 PARTICIPANT DISCONTINUATION/WITHDRAWAL FROM THE STUDY

Participants are free to withdraw from participation in the study at any time upon request.

An Investigator may discontinue or withdraw a participant from the study for the following reasons:

- Withdrawal of informed consent (participant or parent/guardian withdraw for any reason)
- If any clinical Adverse Event (AE), laboratory abnormality, or other medical condition or situation occurs such that continued participation in the study would not be in the best interest of the participant
- Significant study intervention non-compliance
- Disease progression which requires discontinuation of the study intervention
- Requirement of prohibited concomitant medication(s) that requires discontinuation of the study intervention
- Three consecutive VRISE scores < 25 during the 4-week home-based audiovisual IVR stimulation procedure will terminate the investigational intervention.

The reason for participant discontinuation or withdrawal from the study will be recorded in the study "Study termination" CRF. Participants who sign the informed consent form and are randomized but do not receive the study intervention may be replaced. Participants who sign the informed consent form, and are randomized and receive the study intervention, and subsequently withdraw, or are withdrawn or discontinued from the study, will be replaced. The data from participants who are withdrawn or discontinued from the study will be used in the analysis unless the participant requests otherwise.

The Oculus Quest 2 device will be turned off remotely preventing its use by the participant. The participant will return the Oculus Go/Quest including all the equipment (storage box, batteries, remote control, straps) at the final visit.

Withdrawn patients will be replaced to reach a total number of 10 evaluable patients.

Patients will be contacted after 24 hours by phone or email and evaluated for residual virtual-reality symptoms and effects (VRISE questionnaire).

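### Feasibility criterion 3 sits one step beyond the stopping rule on the same VRISE run, so meeting it says almost nothing about tolerability

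*Combined protocol and SAP*

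**What the plan says.** Sections 4.1, 9.1 and the primary-outcome text in section 9.4 list the same four criteria for a successful pilot. Criterion 1 asks for at least 8 of 10 children (80%) to complete. Criterion 2 defines completion as at least 12 of 15 sessions. Criterion 3 is "≤ 3 consecutive VRISE score < 25 per patient during the treatment period". Criterion 4 is "≤ 2 dropouts (20%) for cybersickness (discomfort symptoms experienced in VR").

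The same run of scores is used in two other places:

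- **Stopping.** Section 7.2: "Three consecutive VRISE scores < 25 during the 4-week home-based audiovisual IVR stimulation procedure will terminate the investigational intervention". The adverse-event definitions in section 8.2 agree: "Three (3) consecutive VRISE scores < 25 will lead to the withdrawal of the study", and 8.2.3.1 repeats it. Section 7.2 adds: "The Oculus Quest 2 device will be turned off remotely preventing its use by the participant".
- **Entry.** Section 5.2 excludes a child with "3 consecutive VRIFE scores < 25 at inclusion". Section 2.3 gives the same exclusion under the name VRISE.

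On withdrawn children, section 7.2 says "Withdrawn patients will be replaced to reach a total number of 10 evaluable patients", and also "The data from participants who are withdrawn or discontinued from the study will be used in the analysis unless the participant requests otherwise". Section 9.3 defines the ITT population as everyone registered, and sections 4.1 and 9.4 apply ITT to the primary outcome.

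**The concern.** Criterion 3 tolerates exactly the run that the protocol elsewhere treats as intolerance. Three low scores in a row keep a child out at entry and end treatment at home, yet the same three count as a pass when feasibility is judged. If the stop works as described, the criterion is met whether no child is stopped or every child is.

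At stake is the meaning of one of the stated success thresholds. A report that criterion 3 was met would read as evidence that children tolerated the headset, when it mainly shows that the stopping rule was applied.

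A smaller matter goes with it. Criteria 1 and 4 are written for a denominator of 10, and section 7.2 replaces withdrawn children, so more than 10 may be registered. Neither *dropout* nor *evaluable* is defined.

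**Working it through.** **1. The plan's own figures.** 8/10 = 80% and 2/10 = 20%. The 20% in criterion 4 reproduces only with 10 children: 2/11 = 18%, 2/12 = 17%.

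**2. Criterion 3 with the stop in force.** Let L be a child's longest run of scores below 25 on treatment. Criterion 3 fails if L ≥ 4, and treatment ends when L reaches 3. So L ≤ 3, and the chance of failing is 0 at any low-score rate. Enumerating all 2^15 = 32,768 low/not-low sequences of 15 scores, with stopping at the first run of three, gives a maximum run of 3. No assumption about symptom rates is needed.

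**3. How a fourth low score could still appear.** Sections 3 and 4.1 take the questionnaire before and after each session. The switch-off is remote, and section 4.1 lets block data wait on the device when there is no Wi-Fi. A fourth score is therefore possible if the third is seen late, or if the third is a pre-session score and the child goes on with the session. The 24-hour VRISE check in section 7.2 comes after treatment has ended.

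**4. What criterion 3 passes over.** The documents give no low-score rate. Assuming independent scores at rate r, the chance that at least one of 10 children reaches three in a row is:

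| r (assumed) | 15 scores (after sessions) | 30 scores (before and after) |
|---|---|---|
| 0.05 | 1.5% | 3.3% |
| 0.10 | 11% | 22% |
| 0.20 | 58% | 84% |
| 0.30 | 93% | 99.7% |

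Criterion 3 is met in every cell when the stop is prompt.

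**5. Where such a child is caught instead.** A child stopped before performing 12 sessions is a non-completer under criteria 1 and 2. One stopped later is a completer, so only criterion 4 can register the stop, provided a rule-based stop counts as a dropout.

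**6. Criteria 1 and 4 after replacement.** Suppose k children are stopped before session 12 and replaced, and 10 others complete.

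- k = 2: all registered 10/12 = 83%, criterion 1 met; 2 dropouts, criterion 4 met.
- k = 3: all registered 10/13 = 77%, criterion 1 not met; 3 dropouts, criterion 4 not met.
- Leaving replaced children out, either case would show 10/10 and 0 dropouts.

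With an assumed per-child stop risk q and replacement up to 10 evaluable, P(3 or more stops) = 1 − (1 − q)^10 × (1 + 10q + 55q²). For q = 0.10 this is 1 − 0.3487 × 2.55 = 0.111.

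| q (assumed) | With replacement | Fixed 10, no replacement |
|---|---|---|
| 5% | 2% | 1% |
| 10% | 11% | 7% |
| 20% | 44% | 32% |
| 30% | 75% | 62% |

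These count stops at any time. They are upper bounds for criterion 1, where only stops before session 12 matter. The low end is the more plausible, since section 5.2 screens out sensitive children and section 2.3 reports good tolerability in young children.

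**The case against.** The best defence is that criterion 3 is a loosely drafted echo of the stopping rule and does little harm. This is a 10-child, single-arm pilot with no test on the primary outcome. Criterion 4 glosses cybersickness as discomfort symptoms in VR, so a child stopped by the rule is most naturally a dropout under it, and an early stop also counts against criterion 1. That stands, and it limits the effect on the overall verdict. It does not give criterion 3 any content of its own. The step from stop to dropout is also left to inference: section 7 says that ending training is not the same as leaving the study, so a child stopped late who stays for follow-up could be argued either way.

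Three stronger readings are tempting, and the documents do not support them.

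- A reader might infer that criterion 3 can never fail under the protocol. Pre- and post-session scoring, offline storage and a remote switch-off allow a fourth low score without a clear breach. The zero holds only when the stop takes effect at the third score.
- A reader might infer that excess VR sickness would go unseen. Criteria 1 and 4 would normally show it.
- A reader might infer that replacement lets the trial drop its failures and report 10/10. Sections 4.1, 7, 7.2, 9.3 and 9.4 all point to keeping withdrawn children in the analysis, and criterion 4's limit is a count that needs no denominator. What remains is that the 8/10 and the 20% are not restated for more than 10 children.

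**Conclusion.** The point holds as a wording defect worth fixing. Criterion 3 is set one step past the rule that ends treatment and the rule that bars entry. With a prompt stop its chance of failing is 0, whatever the symptom rate. A fourth low score would depend on transmission delay or on a session begun after a low pre-session score, so meeting the criterion carries almost no information about tolerability.

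The consequence for the feasibility conclusion is modest. On the natural reading criterion 4 catches rule-based stops at any time, and criterion 1 catches those before session 12. The denominator question is mostly a clarification. It would matter from three early stops onward, and only if replaced children were left out against the ITT text. The chance of three or more stops is 2% to 11% at assumed risks of 5% to 10%. The larger figures rest on risks for which the documents give no support.

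**What to change.** In sections 4.1, 9.1 and 9.4:

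- Delete criterion 3 as a separate test.
- In criterion 4, state that any child who reaches three consecutive VRISE scores below 25 during treatment counts as a cybersickness dropout. Allow at most 2 such dropouts among all registered children, including those later replaced.
- Drop the 20% from criterion 4. A floating 20% would pass 3/15, while the count of 2 would not.
- Express criterion 1 as at least 80% of all registered children performing at least 12 of 15 sessions, in line with the ITT rule already stated.
- Leave the safety stop unchanged.

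Do not simply tighten criterion 3 to fewer than three per patient. One stopped child would then fail the pilot, with chance 1 − 0.95^10 = 40% in 10 children at an assumed 5% stop risk. Criterion 4 allows two.

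The cost is wording, with no new data. Rule-based stops count explicitly against feasibility. The fixed limit of 2 becomes a slightly smaller share if children are replaced (2/12 = 17%). Registered children who never start count as non-completers in criterion 1. The change should be made before results are seen.
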